Study Protocol and Statistical Analysis Plan

Title: Improvements in upper extremity function following intensive training are independent of corticospinal tract organization in children with unilateral spastic cerebral palsy: A clinical randomized trial.

NCT: 02918890

Date: 5/1/2014

Study Objectives

This study aims to test the hypothesis that improvements in upper extremity function following either constraint induced movement therapy (CIMT) or bimanual training depend on corticospinal tract (CST) laterality and type of training (unimanual vs. bimanual) in children with unilateral spastic cerebral palsy (USCP). Specifically, we predict that children with a maintained contralateral CST will respond equally to CIMT and bimanual training, while children with ipsilateral CST laterality will be less responsive to CIMT than bimanual training.

Study Design

All study procedures will be approved by the Institutional Review Boards of Teachers College, Columbia University, where the treatments will be conducted, the Burke Medical Research Institute, where TMS evaluations will be performed, and Weill Cornell Medicine, where magnetic resonance imaging (MRI) will be performed.

We will recruit participants from clinics in the NYC area, our website (<http://www.tc.edu/centers/cit/>), ClinicalTrials.gov (NCT02918890), and online support groups. We will obtain written informed consent and assent from children and their caregivers.

We will randomize participants to receive either 90 hours of CIMT or Hand-Arm Bimanual Intensive Training (HABIT) after they complete all baseline outcome measures. Block randomization will be implemented for each cohort of participants, with each cohort stratified by age, sex, baseline hand function and CST connectivity pattern as closely as possible. Randomization will occur offsite using concealed allocation to receive either CIMT or HABIT. Intervention will be delivered in a day-camp model for 6 hours/day over 15 days for a total of 90 hours.

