We will use several measures of hand function to capture different aspects of manual ability. All measures will be administered immediately before treatment (pre-test), within two days after (post-test), and 6 months after treatment (follow-up). Assessments will be administered by an experienced physical or occupational therapist who is blinded to the treatment allocation and CST connectivity of each child.

The primary outcome measures will be the Assisting Hand Assessment (AHA) and Jebsen-Taylor Test of Hand Function (JTTHF). The AHA will measure bimanual hand use, while the JTTHF will measure unimanual dexterity of the affected hand.

AHA: The AHA is a validated test for measuring bimanual hand use in children with UE impairments. The AHA measures the use of the more affected hand in bimanual activities during a play-like testing session. Sessions will be videotaped and scored off-site by a blinded evaluator. The AHA has excellent validity, reliability (0.97-0.99) and responsiveness to change. The AHA units will be used for the analysis. The smallest detectable difference (SDD) for AHA is an improvement of at least 5 units.

JTTHF: The JTTHF measures the time taken to complete six unimanual tasks, which include flipping cards, moving small objects, and lifting cans. The total score is the amount of time taken to complete all tasks. The test will be performed on both the more affected and less affected hands. The JTTHF is well-validated and has excellent reliability.

Several secondary outcome measures will also be used. The Box and Blocks Test (BBT) will measure unimanual dexterity. The Canadian Occupational Performance Measure (COPM) will measure caregiver perceptions of a child's performance of functional goals, and satisfaction with how well the child can perform the goal. The ABILHAND-Kids is a parent-report of child's manual ability. The Pediatric Evaluation of Disability Inventory (PEDI) will be used to measure functioning in the home environment.

BBT: The BBT measures how many blocks (2.5 cm³) an individual can move from one box, over a barrier, to an adjacent box in one minute. Both hands will be tested. The BBT is valid and reliable for children with CP.

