participant will be screened for movement artifact, and slices showing artifact will be removed. Since images are obtained using 65 gradients, up to 30% of slices may be removed without compromising feasibility of tract reconstruction. Using DTI Studio, we will place region of interest seeds in the affected motor cortex and cerebral peduncle, and later in the unaffected motor cortex and cerebral peduncle. We will use tractography to find tracts that pass through both regions of interest. We will categorize each CST as present or absent. If there is a present CST on the affected side, the child will be categorized as having a contralateral CST. If there is not a CST present on the affected side, and a CST present on the other side, the child will be categorized as having an ipsilateral CST.

Statistical Analysis Plan

This will be an intention-to-treat study. If a child misses their 6 month follow-up assessment, we will impute their missing data based on the average change data for other participants in their subgroup. Statistical analyses will be performed using SPSS (IBM). A treatment (CIMT, HABIT) x CST connectivity pattern (contralateral, ipsilateral, bilateral) x test session (pre-, post-, 6 month) ANOVA with repeated measures on test session will be performed on all measures and Newman-Keuls post hoc tests will be performed where appropriate. Regression analyses will be done to determine predictors of outcomes. For children with a bilateral CST, correlations will be done between the LI and changes in outcome measures. Statistical significance will be considered at the $p<0.05$ level.

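### The planned ANOVA fixes the baseline slope at 1 and omits age and sex, which can cost precision, and its average-change imputation inflates type I error when 6-month visits are missed

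*Combined protocol and SAP*

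**What the plan says.** - **Hypothesis (Study Objectives).** Children with a contralateral tract should respond equally to both treatments, while "children with ipsilateral CST laterality will be less responsive to CIMT than bimanual training". This is a treatment x CST interaction in improvement.
- **Allocation (Study Design).** Children are randomised "after they complete all baseline outcome measures", with "each cohort stratified by age, sex, baseline hand function and CST connectivity pattern as closely as possible".
- **Model (Statistical Analysis Plan).** The factors are treatment, "CST connectivity pattern (contralateral, ipsilateral, bilateral") and session: "x test session (pre-, post-, 6 month) ANOVA with repeated measures on test session will be performed on all measures". No covariate is listed, and no term is named as the test of the hypothesis.
- **Missing follow-up (Statistical Analysis Plan).** For a missed 6-month visit, "we will impute their missing data based on the average change data for other participants in their subgroup".
- **Other modelling (Statistical Analysis Plan).** "Regression analyses will be done to determine predictors of outcomes", with no model, outcome form or covariates given.

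The recruitment target is 82. The document gives no pre-post correlation, SD, expected CST group sizes or dropout rate.

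**The concern.** Because the pre-test is a level of session, a treatment difference in improvement that depends on CST pattern can appear only in treatment x CST x session. That term contrasts raw sessions, so post-test minus pre-test and 6 months minus pre-test enter with a baseline coefficient of exactly 1. In a randomised comparison the coefficient can be estimated instead. When the true slope is below 1, this gives a more precise estimate or, if balancing was tight, a standard error that reflects it.

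Of the four balancing factors, CST pattern is in the model and baseline hand function enters, but only as the pre-test level. Age and sex are absent. The key prediction is an interaction in 82 children, about 14 per cell if the cells were equal (82/6 = 13.7), so there is little precision to spare.

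The imputation rule raises a different issue. It adds values with no residual scatter and counts them as observed, which threatens validity rather than precision.

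**Working it through.** **Inputs.** From the document: 82 children, 2 treatments, 3 CST patterns, 3 sessions, significance level 0.05. Assumed: 1:1 allocation, CST groups of 27/27/28, pre-post correlation rho from 0.7 to 0.97, and 8 or 16 missed 6-month visits. The figure of 82 cannot be reproduced, because no effect size, SD or power is stated.

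**1. The planned term.** Its degrees of freedom are (2-1)(3-1)(3-1) = 4, with error (82-6) x 2 = 152.

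**2. Freeing the slope, one visit, equal variances.** In units of SD squared, the variance of change is 2(1-rho) and the baseline-adjusted variance is 1-rho^2. Their ratio is (1+rho)/2, and the SE ratio is its square root. The simulated column uses 6,000 trials with simple allocation within CST pattern.

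| rho | (1+rho)/2 | SE ratio, formula | SE ratio, simulated |
|---|---|---|---|
| 0.7 | 0.850 | 0.922 | 0.928 |
| 0.8 | 0.900 | 0.949 | 0.955 |
| 0.9 | 0.950 | 0.975 | 0.981 |
| 0.95 | 0.975 | 0.987 | 0.994 |
| 0.97 | 0.985 | 0.992 | 0.999 |

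The simulated ratios are about 0.7% higher (0.928/0.922 = 1.007), which is the price of estimating the slope.

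If balancing on the pre-test is tight (pairs matched within CST pattern), the estimates themselves are almost equally precise: the ratio of their actual SDs is 0.987 at rho 0.7 and 0.995 at 0.9. The unadjusted standard error is then too large, because it ignores the balancing. Type I error of the unadjusted contrast is 3.4% and 4.2%, against 4.6-5.2% adjusted. The reported standard error shrinks by a similar amount (ratios 0.921 and 0.975), but the benefit is a correct standard error.

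With unequal variances, let r = SD_post/SD_pre. The slope is rho x r and the SE ratio is sqrt[r^2(1-rho^2)/(r^2 - 2 rho r + 1)]. At rho 0.9 and r = 0.9 this is sqrt(0.1539/0.19) = 0.900. At rho 0.9 and r = 1.1 the slope is 0.99 and the ratio is 1.000, so the gain is gone. The document gives no r, so these are illustrations only.

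**3. Imputation.** Take a child's 6-month score as the pre-test plus the average change of the other children in the same treatment x CST cell. The imputed changes lie on the cell mean and add nothing to the residual sum of squares, but they are counted in the degrees of freedom and the cell sizes. For the 6-month change alone, with missing visits spread evenly, the estimated variance of a cell mean is too small by these factors:
- 8 missing: (68/76) x (74/82) = 0.895 x 0.902 = 0.807, so the SE is about 10% too small.
- 16 missing: (60/76) x (66/82) = 0.789 x 0.805 = 0.635, so the SE is about 20% too small.

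The three-way term also uses complete post-test data, which dilutes this. Simulated type I error (4,000 trials, compound symmetry, missing at random):

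| Missing of 82 | Planned term, rho 0.7 / 0.9 | Mixed model on available data, rho 0.7 / 0.9 |
|---|---|---|
| 0 | 4.8% / 5.2% | 5.2% / 4.9% |
| 8 | 6.9% / 7.8% | 4.8% / 4.7% |
| 16 | 11.4% / 11.2% | 5.0% / 5.6% |

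**4. Averaging the two later visits.** Set the effect so that the planned 4-df term has 80% power under compound symmetry. A 2-df treatment x CST test on the baseline-adjusted mean of both visits then has:
- effect equal at both visits: 94% at rho 0.7, 90% at 0.9;
- effect halved at 6 months: 86% and 79%;
- effect at post-test only: 39% and 34%.

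If post-test and 6-month scores correlate 0.95 with each other and 0.9 with the pre-test (effect size fixed, 4,000 simulated trials), planned versus averaged power is 76% versus 77% for a sustained effect, 63% versus 49% if it halves, and 85% versus 25% if it is present at post-test only.

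**The case against.** The strongest reply is that with complete data the planned treatment comparison is unbiased, and the gain from adjustment may be negligible. Outcome Measures gives AHA reliability of 0.97-0.99. Reliability is not the correlation across training, but it makes a high one plausible. At rho of 0.95 or more the gain is under 1%. This stands for the AHA. It does not settle the JTTHF, for which no reliability figure is given and whose score is a time ("The total score is the amount of time taken to complete all tasks").

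The planned regression might include age and sex. As written, though, it concerns predictors of outcome and specifies no adjusted treatment comparison.

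Three stronger readings are tempting and are not supported:
- **That the model ignores the balancing factors.** CST pattern is a factor and baseline performance is a session level. Only age and sex are wholly absent.
- **That a 2-df test averaged over visits is simply more powerful than the 4-df term.** Study Objectives does not say whether the difference should last to 6 months. The gain needs a sustained effect, and step 4 shows how far it reverses.
- **That the planned test is invalid even with complete follow-up.** Under compound symmetry it holds its 5% level. At correlations 0.9 and 0.95 it rose to about 6.0% uncorrected and was 4.9% with a Greenhouse-Geisser correction. The plan is silent on any correction, so this is not the main point.

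It is also fair to say that imputation and adjustment are separate matters. They are sized separately here and share one remedy.

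**Conclusion.** The concern holds in two parts.

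**Precision.** The fixed slope costs about 7% in standard error at rho 0.7, 2% at 0.9 and almost nothing at 0.95 or more. This assumes equal variances and near-equal CST groups. If balancing on baseline was tight, the planned test is mildly conservative instead. Any gain from age and sex depends on their prognostic value, which is not given.

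**Validity when visits are missed.** Type I error of the three-way test rises from 5% to about 7-8% with 8 of 82 missing and about 11% with 16. This is the stronger reason to act. It rests on reading subgroup as treatment x CST cell, on data missing at random, and on missing counts that are assumptions.

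The mixed-model error rates above come from a model with the pre-test covariate; the version that also includes age and sex was not simulated with missing visits. No general power advantage is claimed for averaging the two visits.

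**What to change.** In the Statistical Analysis Plan:

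1. Analyse post-test and 6-month scores in a mixed model for repeated measures, with an unstructured within-child covariance and a small-sample degrees-of-freedom method such as Kenward-Roger. Include the same measure's pre-test score, age and sex as covariates, and treatment, CST pattern, session and their interactions.
2. Use all available data in place of the average-change imputation.
3. Prespecify the ipsilateral-minus-contralateral difference in treatment effect as the key contrast, at a visit or visit average that the sponsor chooses and justifies in advance. The average should not be imposed as the confirmatory test.
4. Keep the planned ANOVA as supportive.
5. Report change scores for comparisons between the CST groups. These groups are not randomised, and adjusted and change-score analyses answer different questions if they differ at baseline.

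**Cost.** Only SAP wording changes. No new data are needed, since pre-test, age, sex and CST pattern are known before allocation. The model spends a few degrees of freedom, gains little or nothing from adjustment at rho of 0.95 or more, and assumes that missing 6-month data are missing at random. If the sponsor chooses the visit average, it gives up substantial power should the effect be gone by 6 months.

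### The predicted equal response in contralateral children has no decision rule beyond p<0.05, and Newman-Keuls does not control familywise error for CIMT-HABIT differences across the CST patterns

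*Combined protocol and SAP*

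**What the plan says.** Study Objectives makes two predictions. The first is "Specifically, we predict that children with a maintained contralateral CST will respond equally to CIMT and bimanual training". The second is that "children with ipsilateral CST laterality will be less responsive to CIMT than bimanual training".

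The Statistical Analysis Plan specifies "A treatment (CIMT, HABIT) x CST connectivity pattern (contralateral, ipsilateral, bilateral) x test session (pre-, post-, 6 month) ANOVA". It describes this as an "ANOVA with repeated measures on test session will be performed on all measures and Newman-Keuls post hoc tests will be performed where appropriate". The only decision rule is "Statistical significance will be considered at the $p<0.05$ level". It does not say which means Newman-Keuls compares (six treatment-by-CST change means, or up to 18 session means) or what must be significant before it is run.

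Outcome Measures names AHA and JTTHF as joint primaries, each measured before treatment, within two days after it, and at 6 months. Neither section says which session decides or how a split between the two outcomes is read. For missed 6-month visits, "we will impute their missing data based on the average change data for other participants in their subgroup". Randomization is by cohort, "with each cohort stratified by age, sex, baseline hand function and CST connectivity pattern as closely as possible", so within-pattern comparisons of CIMT with HABIT are randomized comparisons in roughly balanced arms.

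**The concern.** The two predictions need different evidence. A difference can be supported by a small p-value. Equality cannot be supported by a large one, because a small subgroup gives non-significance whether or not the arms differ. If the contralateral comparison comes out at p>0.05, the plan has nothing that separates arms shown to be similar from too few children to tell. The document's own AHA benchmark is a smallest detectable difference of 5 units, so the question is whether the data could exclude a difference of that size.

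Newman-Keuls raises a separate issue. It holds familywise error when all means are equal, but not when the means form separate clusters. Three CST patterns, each with a CIMT and a HABIT mean, can form such clusters, and the study hypothesis itself has response depend on CST laterality. A false CIMT-HABIT difference in some pattern could then be reported at more than the nominal 5%.

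**Working it through.** The plan gives no power or error figure for this point. The target of 82 cannot be re-derived, because the documents state no effect size, SD, power or target contrast for it. Nothing below depends on how 82 was reached.

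**Inputs.** From the documents: 82 children, two arms, three CST patterns, alpha 0.05, AHA smallest detectable difference 5 units. Assumed: SD of AHA change 5-8; 14-18 contralateral children per arm (82/6 is about 14; 18 allows for a larger contralateral group).

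**1. What non-significance can exclude.** The half-width of the 95% interval is t × SD × √(2/n), with 2n−2 degrees of freedom.
- n=18, SD 5: 2.032 × 5 × √(2/18) = 2.032 × 1.667 = 3.39 units.
- n=14, SD 8: 2.056 × 8 × √(2/14) = 2.056 × 3.024 = 6.22 units.

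The chance of missing a true 5-unit difference follows from the noncentral t with noncentrality 5/(SD√(2/n)).
- n=18, SD 5: noncentrality 3.00, missed 17.0%.
- n=14, SD 8: noncentrality 1.65, missed 64.3%.
- Widening to 8-20 per arm: half-width 3.2-8.6 units, missed 13-79%.

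**2. Newman-Keuls over six change means.** Simulation: 20,000 runs per scenario, 14 per cell (84 children, close to 82), pooled error on 78 df, step-down studentized-range tests at 0.05. The gap is the assumed distance between neighbouring CST-group means in within-cell SDs; no document gives one. With no treatment effect and no gate:

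| Gap (SD) | Any false CIMT-HABIT difference, one outcome | Same, either primary counts | False ipsilateral claim favouring HABIT, either primary counts |
|---|---|---|---|
| 0 | 2% | about 3% | 0.6% |
| 0.5 | 6% | 10-12% | 2.1-2.5% |
| 1 | 13% | 21-25% | 4.0-4.6% |
| 2 | 14% | 23-26% | 4.1-5.0% |

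Ranges are for a correlation of 0.7 down to 0 between the primaries. The upper limits follow by hand. Once clusters are well separated, each pair is tested as two adjacent means at an unadjusted 5%:
- three pairs, one outcome: 1 − 0.95³ = 14.3%;
- three pairs, two uncorrelated outcomes: 1 − 0.95⁶ = 26.5%;
- ipsilateral pair in the predicted direction, two uncorrelated outcomes: 1 − 0.975² = 4.9%.

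**3. With a gate.** If Newman-Keuls runs only after a significant treatment-by-CST interaction, then for one outcome:
- no treatment effect: 1 to about 4%, since the gate itself opens only about 5% of the time;
- a real 1-SD ipsilateral effect with gaps of 1-2 SD: about 4-6% for the patterns with no effect, and 6.8% in one layout with a 1.5-SD gap;
- a 2-SD ipsilateral effect with a 3-SD gap: the gate opens in 97% of runs and the error is 9.6%, near its limit of 1 − 0.95² = 9.75%.

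With unequal cells (12, 20 and 9 per arm) the last two settings give 8.9% and 13.8%. Part of that comes from using the harmonic mean of the cell sizes.

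**4. Holm.** One family of six comparisons (three patterns by two primaries) keeps familywise error at about 3-5% in the balanced scenarios run.

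**The case against.** Four points can fairly be made for the plan.

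- **The main hypothesis has a test.** The treatment by CST by session term tests whether response depends on both. This stands, and the ANOVA should stay. It does not show that the contralateral arms are equal.
- **The wording on post hoc tests conventionally implies a significant interaction first.** On that reading, the error with no treatment effect and one outcome is under 5%. This stands as far as it goes. The gate is not written down, and it protects least when a real ipsilateral effect opens it.
- **The inflated rates count the wrong claim.** Any-pair error includes bilateral children, for whom nothing is predicted, and contralateral children, where a false difference would contradict the prediction. This stands. A reader might infer that the trial's directional prediction runs up to a 26% false-positive risk. It does not: that claim stays at or below about 5%, even ungated with either primary counting. The 26% also needs gaps of about 2 SD or more, which are a state of nature and not an analysis choice, together with uncorrelated primaries and an either-counts reading.
- **Post-test and Holm are choices among several.** This also stands. What matters is that a session is named and that the procedure has strong control.

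A reader might also take the title, "Improvements in upper extremity function following intensive training are independent of corticospinal tract organization", to mean that the plan commits to accepting a null moderation result. The Statistical Analysis Plan contains no such analysis. The title shows only that the same rule would be needed if that claim were made.

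**Conclusion.** The concern holds in two parts of different strength.

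The firm part is equality. The first prediction has no rule other than p<0.05, and that omission needs no assumption to see. Its size does: with SD 5-8 and 14-18 per arm, a difference as large as the AHA smallest detectable difference would be missed 17-64% of the time and could be reported as equal response.

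The Newman-Keuls part is conditional. It concerns claims of a CIMT-HABIT difference in any CST pattern, and it depends on how far apart the CST groups lie and whether the tests are gated. For one outcome the error runs from about 2% to 14% ungated. Gated, it is 1 to about 4% with no effect and about 4-6% with a real 1-SD ipsilateral effect. The documents support neither a claim that the directional ipsilateral prediction is exposed to excess error, nor a claim that the planned ANOVA is wrong.

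This should be fixed before analysis, and the change is cheap.

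**What to change.** 1. Keep the ANOVA as the general test. For AHA and JTTHF, report with 95% confidence intervals the contralateral and ipsilateral HABIT-minus-CIMT differences in change, and the ipsilateral-minus-contralateral difference between them. Claim equal response only if the 90% interval of the contralateral difference lies inside a margin justified in advance for that outcome. Apply the same rule to the ipsilateral-minus-contralateral estimate before any claim of independence from CST organization. Otherwise report that a difference was not shown. The 5-unit AHA value is only a candidate margin, because it describes detectable change and is not presented as a between-arm difference. JTTHF needs its own.
2. For CIMT-HABIT comparisons within CST patterns on the two primaries, replace Newman-Keuls with Holm over the six comparisons, or another procedure with strong familywise control. Claim a result only for the outcome on which it is significant. For other post hoc comparisons and the secondary measures, also use a strong-control procedure or label them exploratory.
3. In the same edit, name the deciding session. Post-test is one reasonable choice, because it does not rely on the imputation of 6-month data; an effect seen only at 6 months would then be secondary.

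**Cost.** The changes are to wording only, but two consequences should be accepted openly.

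- Equality may not be demonstrable with 82 children. With a 5-unit margin, arms truly equal and 14-18 per arm, the AHA contralateral comparison passes 6-80% of the time and the AHA ipsilateral-minus-contralateral estimate 0-35%.
- With 14 per arm and gaps of 1-2 SD, Holm over six comparisons detects a 1-SD ipsilateral effect about 50% of the time on a given outcome, against 73-74% for ungated and 43-44% for gated Newman-Keuls. For 0.625 SD (5 units at SD 8) the figures are 16%, 36-38% and 16-17%. Power therefore falls against ungated Newman-Keuls when the CST groups are well separated, and is about equal to or above the gated version.

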The inclusion criteria will be: 1) ages 6 to 17 years, 2) diagnosed with USCP 3) capable of participating in a 15 day, 6 hours/day day camp while separated from caregiver(s), 4) capable of following directions regarding hand use and testing, 5) capable of communicating needs, 6) mainstreamed in age-appropriate school classroom, and 7) able to lift the more affected arm 15cm above a table surface and grasp light objects. The exclusion criteria will be: 1) unwillingness to comply with instructions or other behavioral issues making delivery of an intensive therapy infeasible, 2) health problems unassociated with hemiplegia, 3) visual impairment that could interfere with participation, 4) orthopedic surgery on the more affected hand within 1 year, 5) presence of metallic objects in the body, and 6) botulinum toxin in the more affected upper extremity within the past 6 months or intended treatment within the study period, 7) seizures after the age of 2 years, 8) family history of seizure disorders, 9) current medication use to lower the seizure threshold, 10) claustrophobia, or 11) pregnancy.

We aim to recruit 82 participants based on sample size calculations from results of the Assisting Hand Assessment (AHA) and Jebsen-Taylor Test of Hand Function (JTTHF) outcomes of a prior CIMT/HABIT randomized controlled trial and pilot data.

Methodology

Children will participate in an intensive hand training intervention using either one (CIMT) or both (HABIT) hands. During the intervention, children will be paired with a trained interventionist, with an interventionist:child ratio of at least 1:1. We will recruit and train physical and occupational therapists, graduate students in kinesiology/neuroscience, speech pathology, and psychology, and undergraduates to be interventionists. Interventionists will be supervised by experienced PT/Ots. Both the interventionists and supervisors will be blinded to CST connectivity patterns. Prior to the intervention, a training session will be conducted by the supervisors for standardization based on the established manual of procedures for CIMT and HABIT. Fidelity will be reinforced by supervisors during the day camp and daily post-camp meetings. Participants receiving CIMT and HABIT will be located in separate rooms, with each room being supervised by experienced PTs/OTs who will model and ensure uniformity of treatment. Each day, interventionists will attend team meetings to discuss the progress and needs of each child.

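### The plan does not say how sphericity is handled in its three-session ANOVA; if the uncorrected F is used, the key interaction is tested at between 5.0% and about 9.5%

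*Combined protocol and SAP*

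**What the plan says.** The Statistical Analysis Plan section names one main model for every outcome, treatment (2 levels) by CST pattern (3 levels) by session (3 levels): "ANOVA with repeated measures on test session will be performed on all measures and Newman-Keuls post hoc tests will be performed where appropriate". For the post hoc tests, neither the factor nor the error term is given. On software it says "Statistical analyses will be performed using SPSS (IBM"), and on the threshold "Statistical significance will be considered at the $p<0.05$ level".

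The Outcome Measures section times the assessments "immediately before treatment (pre-test), within two days after (post-test), and 6 months after treatment (follow-up"). A child who misses the 6-month visit stays in the analysis, because the investigators will "impute their missing data based on the average change data for other participants in their subgroup".

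The Study Objectives section predicts that the advantage of one training type over the other depends on CST laterality. In this model that prediction is the treatment by CST by session interaction. No section mentions sphericity, a test for it, an epsilon adjustment, a multivariate test or a covariance structure.

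**The concern.** With three repeated sessions, the ordinary F test for any effect involving session keeps its nominal level only if the three session differences (pre to post, pre to 6 months, post to 6 months) have equal variance. Pre and post lie either side of a 15-day camp, and follow-up is 6 months later. Equal variances are therefore doubtful, though the documents do not settle it.

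The affected test carries the trial's hypothesis and is run on both primary outcomes, the AHA and the JTTHF. If the assumption fails and no correction is used, a true null interaction is rejected too often. Because the plan is silent, the choice among uncorrected, corrected and multivariate results is also left open until the data are seen.

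The same assumption lies behind Newman-Keuls in its usual form, which applies one pooled error to every pair of sessions. An epsilon-adjusted F does not change those pairwise tests.

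**Working it through.** **Inputs from the documents.** N = 82 (Study Design: "We aim to recruit 82 participants based on sample size calculations from results of the Assisting Hand Assessment (AHA") and the JTTHF); 2 x 3 = 6 between-child cells; 3 sessions; threshold 0.05. The figure of 82 cannot be rebuilt, because no effect size, SD, power or dropout rate is given.

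**Assumed inputs.** Between-session correlations, equal SDs across sessions, normal data, and the fraction missing at 6 months.

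**1. Degrees of freedom.** Interaction: (2-1)(3-1)(3-1) = 4. Error: (82-6)(3-1) = 152. The uncorrected test refers F to F(4, 152).

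**2. Epsilon.** Box epsilon = (sum of lambda)^2 / (2 x sum of lambda^2), where the two lambdas are the eigenvalues of the covariance matrix of the orthonormal session contrasts. It is 1 under sphericity, and its floor for three sessions is 1/(3-1) = 0.5.

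**3. Level by epsilon.** Simulated null distribution of the uncorrected three-way F, 1,000,000 draws per value:

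| Epsilon | Actual level |
|---|---|
| 1.0 | 5.0% |
| 0.90 | 5.6% |
| 0.80 | 6.4% |
| 0.735 | 6.9% |
| 0.66 | 7.6% |
| 0.60 | 8.3% |
| 0.5 (floor) | 9.5% |

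The plan's 5% is reproduced at epsilon 1. A level of about 6 to 8% corresponds to epsilon of about 0.85 to 0.62.

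**4. Epsilon from assumed correlations** (pre-post / pre-6 month / post-6 month):

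| Correlations | Epsilon | Uncorrected level |
|---|---|---|
| .90/.90/.90 | 1.00 | about 5% |
| .95/.95/.97 | 0.91 | 5.6% |
| .90/.81/.90 | 0.82 | 6.2% |
| .90/.85/.95 | 0.75 | 6.8% |
| .80/.80/.95 | 0.69 | 7.3% |
| .70/.70/.95 | 0.63 | 8.0% |

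Worked case .90/.85/.95: each difference variance is 2(1 - r), giving 0.2, 0.3 and 0.1. The contrast covariance matrix has 0.1 on the diagonal and 0.0577 off it, so the lambdas are 0.1577 and 0.0423. Epsilon = 0.2^2 / (2 x 0.02667) = 0.75.

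**5. Corrected tests, complete data.** Simulations of 10,000 runs each, at epsilon 0.75, 0.69 and 0.63 with near-equal cells, gave 6.8%, 7.1% and 7.7% uncorrected. Greenhouse-Geisser gave 5.0%, 5.0% and 4.9%, and the multivariate (Wilks) test 5.1%, 5.1% and 4.3%. With unequal cells (16, 18 and 7 per arm) the uncorrected level was 7.0 to 8.0%, Greenhouse-Geisser 5.1 to 5.5% and Wilks 5.0 to 5.1%.

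**6. Session contrasts with a pooled error.** The ratio of true to pooled SE is the square root of a pair's difference variance over the mean of the three.
- .95/.75/.75: variances 0.1, 0.5, 0.5; mean 0.367. Pre-post: sqrt(0.1/0.367) = 0.52, so the pooled SE is too large. Pre-6 month: sqrt(0.5/0.367) = 1.17, so it is too small, and a single two-sided 5% z-test runs at 2 x P(Z > 1.96/1.17), about 9%.
- .75/.75/.95: variances 0.5, 0.5, 0.1. Pre-post is now 1.17, so the pooled SE is too small for that pair.

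**7. With the planned imputation.** Each missing 6-month value was set to the child's pre-test value plus the mean change in the child's cell, with values missing at random.

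| Correlations | Assumed missing | Uncorrected | Greenhouse-Geisser |
|---|---|---|---|
| .90/.90/.90 | 10% | 7.5% | 7.2% |
| .90/.90/.90 | 20% | 11.7% | 11.1% |
| .90/.85/.95 | 10% | 9.6% | 8.2% |
| .90/.85/.95 | 20% | 15.1% | 13.5% |

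Over all patterns run at 10% missing, Greenhouse-Geisser left about 7 to 9%. Interaction tests on each child's own observed change, without imputation, held 4.3 to 5.8%.

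**The case against.** The strongest reply is that silence is not an error. The plan does not say that the uncorrected line will be reported, and a repeated-measures analysis commonly prints corrected results beside it. Nothing in the documents fixes epsilon. The AHA reliability of 0.97 to 0.99 given under Outcome Measures allows high correlations between sessions, and with .95/.95/.97 the level is only 5.6%. Newman-Keuls might be used to compare CST patterns or treatment-by-CST cells and never touch sessions.

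Most of this stands, and it limits the point. Three stronger readings are tempting but not supported:

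- **That the interaction is tested at 6 to 8%.** This needs both the uncorrected row and an epsilon of about 0.85 to 0.62. The documents give neither.
- **That the immediate pre-to-post effect is judged with too large a standard error.** This holds only if pre and post are the most correlated pair. If post and 6 months are the closest pair, the direction reverses (step 6).
- **That the mean-change imputation makes non-sphericity worse.** In the non-spherical patterns tried, imputation raised epsilon (for .95/.75/.75, from 0.65 to 0.67 at 10% missing and 0.69 at 20%). It inflates the error rate by another route: imputed values are treated as observed, so the error term is understated.

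The reply does not remove the gap. Having several results in the output is not the same as choosing one in advance, and a corrected F row leaves pooled-error pairwise tests as they were.

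**Conclusion.** The point holds in conditional form. The plan's central test depends on an assumption that the visit spacing makes doubtful, and the plan does not say how that assumption is handled. If the uncorrected F is used, the level at N = 82 is between 5.0% and about 9.5%; over the moderate range of epsilon the excess is 1 to 3 percentage points. That range rests on normal data, complete follow-up and cells of 13 or 14. Where epsilon falls within it cannot be known from the documents.

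The point about post hoc tests is conditional on two things the plan does not state: that Newman-Keuls is applied to sessions, and that it uses pooled error. If so, standard errors are too small for the less correlated pairs and too large for the more correlated ones. Which pairs these are is unknown.

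This is a modest error-rate problem, but it affects the main hypothesis on both primary outcomes and is cheap to remove, so it should be fixed.

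**What to change.** **Preferred.** Replace the ANOVA with a mixed model with treatment, CST pattern, session and their interactions, and an unstructured covariance over the three sessions. Fit it to all observed data and drop the subgroup-mean imputation; a child without a 6-month visit still contributes pre and post. Replace Newman-Keuls for sessions with two contrasts, post minus pre and 6 month minus pre, each with its own standard error and Holm-adjusted (smaller p-value against 0.05/2 = 0.025, the other against 0.05). The model assumes neither sphericity nor imputed values, but it does assume that missingness is at random given the observed data.

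**If the ANOVA is kept.** State that every test involving session uses the Greenhouse-Geisser row (or the multivariate test, naming one), and base session comparisons on each child's own observed change. This alone does not restore 5% if 6-month values are still imputed as planned (step 7).

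**Cost.** A few sentences in the plan and no new data. The downside is slightly fewer degrees of freedom if sphericity does hold.
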